StenTing foR ischemic strokes secondary to medIcally refraCTory IntraCranial

atherosclerotic diSease: STRICT-ICAS

January 03, 2025

[name], [name]

NCT06790147

Study Title: StenTing foR ischemic strokes secondary to medIcally refraCTory IntraCranial atherosclerotic diSease: STRICT-ICAS

Principal Investigators: [name]; [name]

Institute Name and Address:

Semmes Murphey Foundation [name]

Collaborators: up to 10 centers.

Background and Rationale

Intracranial atherosclerotic disease (ICAD) accounts for approximately 10% of ischemic strokes in the United States and is a major cause of recurrent strokes. Although three randomized controlled trials (RCT) have failed to show the benefit of endovascular treatment [1-3], there exists a subset of patients who experience recurrent strokes despite maximum medical therapy. These patients may benefit from Percutaneous Angioplasty and Stenting (PTAS), especially when selecting flow-related stroke subtypes rather than perforator or embolic strokes or patients with recurrent transient ischemic attacks. A follow-up post-market surveillance study mandated by the FDA to evaluate peri-procedural safety of the Wingspan Stent (Stryker, Kalamazoo, MI) demonstrated reduced perioperative stroke and death rates, further suggesting that patients could benefit from PTAS.[4] The experience of neurointerventionalists and proper patient selection were the main reported factors for a lower periprocedural stroke and death rate in the WEAVE trial in comparison to the SAMMPRIS trial.

The practice pattern of endovascular treatment for medically refractory ICAD has been evolving since the publication of the WEAVE trial with an increasing off-label utilization of balloon-mounted coronary stents or other self-expanding stents. Since the publication of the three negative RCTs, there has been a lack of prospective data regarding current endovascular practice patterns for ICAD. There is likely variation in patient selection, timing of intervention, and devices used. Analyzing these may provide insight into optimal practices for the endovascular treatment of ICAD and the design of future trials.

Study Purpose: Establish a prospective multicenter registry of the patients undergoing intracranial stenting for ischemic strokes caused by medically refractory ICAD to evaluate current practice pattern, periprocedural and delayed outcomes.

Study Design: Prospective, multicenter, single arm, observational study

Study Population: Consecutive patients with ischemic strokes caused by medically refractory ICAD undergoing intracranial stenting, and meeting study inclusion criteria will be included.

Study Intervention/Product and its Intended Use: Participating centers will follow their standard of care protocols for intracranial stenting for medically refractory ICAD. We will not advertise use of any specific on-label or off-label device for intracranial stenting. No new products will be studied or promoted.

Study Duration: 2 years

Inclusion Criteria (adopted from [4])

- Adult patients with ICAD resulting in 70-99% vessel stenosis who undergo PTAS with any device will be included.
- Patients will have to experience a stroke despite medical management involving risk factor modification and an antiplatelet agent.
- Baseline modified Rankin Scale (mRS) ≤ 3
- Performance of the endovascular procedure at least 3 days after the last stroke.

Exclusion Criteria:

- Large vessel occlusion strokes undergoing rescue intracranial stenting will not be included
- Baseline modified Rankin Scale (mRS) >3
- Performance of the endovascular procedure less than 3 days after the last stroke.
- Patients undergoing intracranial stenting for first stroke caused by ICAD
- Adult patients with ICAD resulting in <70% vessel stenosis

Objectives and Endpoint:

Aim 1: To establish a prospective multicenter registry evaluating current endovascular practice patterns of patients undergoing PTAS for medically refractory ICAD.
Hypothesis 1: A variety of devices besides the Wingspan stent system (Stryker Neurovascular, Fremont, CA, USA) will be used for PTAS, including off label use of coronary balloon-mounted stents or Neuroform atlas stents

Aim 2: To establish a prospective multicenter registry evaluating current periprocedural and delayed outcomes for PTAS in patients with medically refractory ICAD.

Hypothesis 2a: The periprocedural stroke, bleed, and death rate will be similar to that published in the WEAVE trial.[4]

Hypothesis 2b: The 1-year follow-up rates of stroke within the target artery territory, non-traumatic hemorrhage, or neurologic death will be similar to that published in the WOVEN trial.[5]

Outcomes:

The primary outcomes will include:

- Recurrent ischemic stroke within the territory treated, intracranial hemorrhage, or death within 72 hours after the procedure. All of the patients enrolled in the trial will be assessed at 72 hours post-stenting either in the hospital by the study interventionalist or, if the patient had already been discharged home, by telephone interview by a core study nurse or interventionalist
- 2. Stroke within the territory treated, intracranial hemorrhage, or neurologic death within 6 months to 1 year after PTAS. All the patient enrolled in the trial will undergo
 - Follow up clinic visit between 6 months to 1 year per standard of care
 - Follow up vascular imaging (modality of imaging will be decided based on standard of care at participating centers)
- 3. Secondary outcomes will include-
 - Stent patency on follow up vascular imaging
 - Re-stenosis ≥ 70% on follow up vascular imaging

- mRS between days 180-360 after the procedure
- Any death within 1 year after the procedure
- Myocardial infarction within 72 hours after the procedure.

Variables collected

Age, sex, race, comorbidities (hypertension, hyperlipidemia, diabetes, coronary artery disease), smoking status, baseline mRS, affected artery, number of prior strokes attributable to target lesion, type of stroke (embolic, borderzone, perforator, etc.), degree of stenosis of target lesion, Mori classification, medical management for ICAD, type of antiplatelets, P2Y12 test value, aortic arch type, proximal tortuosity, collaterals, device used for PTAS, plaque anatomy, diameter of proximal and distal vessels, type of anesthesia, intraprocedural blood pressure, use of anticoagulation or IV antiplatelet therapy intraprocedurally, clinical status at 72 hours, periprocedural antiplatelet regimen, intraprocedural and post procedural complications, degree of residual stenosis, follow up vascular imaging data between 6-12 months post procedure, follow up clinical data between 6-12months post procedure.

Sample Size: 150 patients

Safety Considerations and Adverse Event Reporting: Will be done according to standard of care at participating centers

Ethics and Regulatory Consideration: IRB approval will be taken at all participating centers. We will encourage centers to request waiver of informed consent process as we will be obtaining deidentified data regarding current practice pattern by following standard of care at participating centers.

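### Is it an error to expect a mixed-device registry of 150 patients to show event rates similar to the Wingspan benchmarks?

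*Protocol*

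**What the plan says.** Under Objectives and Endpoint, Aim 2 is to evaluate current periprocedural and delayed outcomes of stenting in medically refractory disease. Hypothesis 2a reads: "The periprocedural stroke, bleed, and death rate will be similar to that published in the WEAVE trial". Hypothesis 2b says that the one-year rates "will be similar to that published in the WOVEN trial".

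The protocol identifies both comparators as Wingspan studies. Background and Rationale describes the first as a post-market study "to evaluate peri-procedural safety of the Wingspan Stent", and the titles in the Bibliography give 152 on-label patients for WEAVE and name Wingspan for WOVEN.

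The registry is broader. The Inclusion Criteria admit adults "who undergo PTAS with any device will be included", and Hypothesis 1 expects a variety of devices besides Wingspan, "including off label use of coronary balloon-mounted stents or Neuroform atlas stents". The criteria are nevertheless marked as adopted from the WEAVE publication.

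On devices, Background and Rationale says "There is likely variation in patient selection, timing of intervention, and devices used" and adds that analysing these differences may be informative. Variables collected lists "device used for PTAS". The design is single-arm and observational, and Sample Size is given as 150 with no derivation.

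**The concern.** Two features catch the eye.

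The first is the device mix. If Hypothesis 1 is right, the rate in 2a and 2b is an average over Wingspan and several other stents, while the benchmarks come from Wingspan alone. One pooled figure cannot show whether any similarity holds for Wingspan, for the other devices, or for both. Readers might carry a reassuring pooled result over to an off-label device whose own rate is quite different.

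The second is precision. A 72-hour composite is likely to be uncommon, and 150 patients yield few events. An observed rate equal to the benchmark could be called similar while the data remain compatible with about twice the harm.

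If the protocol claimed equivalence for each device, or rested its sample size on such a claim, either point would be serious.

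**Working it through.** **Inputs.** From the protocol: n = 150 (Sample Size), a 72-hour window for the first primary outcome, and 152 patients in WEAVE (Bibliography). The protocol prints no benchmark rate, margin, alpha or power, so it contains no sample-size figure to reproduce. Assumed: 72-hour benchmark rates p0 of 2%, 4% and 6%, one-year rates of 8% to 12%, and a doubling as the yardstick. The document uses none of these.

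**Step 1: interval when the observed rate equals the benchmark.** With x = 150 × p0 events, the exact (Clopper-Pearson) limits are the 2.5% quantile of Beta(x, n − x + 1) and the 97.5% quantile of Beta(x + 1, n − x).

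| p0 | x/150 | exact 95% CI | 2 × p0 | doubling excluded? |
|---|---|---|---|---|
| 2% | 3 | 0.41–5.73% | 4% | no |
| 4% | 6 | 1.48–8.50% | 8% | no |
| 6% | 9 | 2.78–11.08% | 12% | yes |

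At 4% the answer depends on the convention: the one-sided 95% exact upper limit for 6/150 is 7.74%, below 8%. At 2% it stays above the doubled rate (5.09% against 4%).

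**Step 2: how often a doubling would be excluded.** Let c be the largest count whose two-sided 95% upper limit lies below 2 × p0. If the true rate is p0, the chance of excluding a doubling is P(X ≤ c) with X ~ Bin(150, p0).

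- p0 = 2%: c = 1, probability 0.196
- p0 = 4%: c = 5, probability 0.442
- p0 = 6%: c = 10, probability 0.710

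At assumed one-year rates of 8%, 10% and 12%, with all 150 followed, it is 0.854, 0.928 and 0.965. The precision point therefore concerns Hypothesis 2a alone.

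**Step 3: how often a truly doubled rate would look no worse than the benchmark.** P(X ≤ 150 × p0) with X ~ Bin(150, 2 × p0) is 0.146, 0.040 and 0.011 at p0 = 2%, 4% and 6%. A plainly misleading point estimate is uncommon except at the lowest assumed rate.

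**Step 4: what a device split would show.** Take an invented 75/75 split of 6/150 (4.0%) into 1/75 and 5/75:

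- 1/75 = 1.3%, exact 95% CI 0.03–7.21%
- 5/75 = 6.7%, exact 95% CI 2.20–14.88%

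Fisher's exact test gives p = 0.21, so even this contrast is compatible with chance. An even split, 3/75, has a CI of 0.83–11.25%. Its upper limit is 11.25/4.0 = 2.8 times the observed rate, against 8.50/4.0 = 2.1 times for 6/150.

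**Step 5: compare with what the protocol commits to.**

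- *Sample size.* No rate, margin or power is attached to 150, so Steps 1 and 2 contradict no stated figure.
- *Question asked.* Aim 2 and both hypotheses speak of stenting in this population, not of a stent. Whether current mixed practice reaches the published rates is a legitimate question, and the any-device rate is the quantity that answers it.
- *Basis for comparability.* Eligibility is adopted from WEAVE. The Background says of that trial's lower rate than SAMMPRIS: "The experience of neurointerventionalists and proper patient selection were the main reported factors for a lower periprocedural stroke and death rate". On the protocol's own account, the main drivers were operators and patient selection rather than the device.
- *Reporting.* Nothing says that only a pooled rate will be shown. Device is collected, and device variation is named as something to analyse.

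**The case for a change.** The strongest case for the concern is that no SAP can change what 150 patients can exclude, and that the word similar stands in the protocol itself, attached to primary outcomes and named benchmarks, with a leading journal as the publication target. An equal 72-hour rate could be written up as similar although twice the rate had not been ruled out.

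The arithmetic behind this stands at the low end of the assumed range, and it is a fair caution for whoever writes the report. It does not make the protocol wrong. The protocol attaches no decision rule to similarity, so no stated inference fails. The factor of two and the 2–4% range come from outside the document, and the result changes at 6%, or at 4% with a one-sided limit.

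It is also true that a pooled rate cannot say for which device similarity holds. But the hypotheses make no such claim. A Wingspan row and an all-other-devices row would not settle the matter: the second would still pool coronary balloon-mounted stents with Neuroform Atlas stents, both would be less precise than the overall rate, and because centers choose the device, neither could be read as a device comparison.

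**Conclusion.** Not a finding. Hypotheses 2a and 2b are loosely worded expectations in a descriptive single-arm registry. They contradict no other statement or figure in the protocol, and setting an any-device rate beside the published rates is a legitimate use of the data. Exact intervals, the benchmark's own interval, the sense in which similarity may be claimed, and a breakdown by device are reporting details commonly left to the SAP, and the variable needed for the breakdown is already collected.

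What remains is a caution on interpretation. If the 72-hour benchmark lies at about 2–4%, an equal rate in 150 patients leaves a two-sided 95% upper limit of 2.9 to 2.1 times that rate. This rests on assumed benchmark rates, and it does not carry over to 2b at assumed rates of 8–12%. It bears on how a result is phrased, not on the validity of the design, the sample size or the data collected.

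### Hypothesis 2b needs a 1-year event rate, but primary outcome 2 and its single clinic visit in months 6-12 do not secure status at 12 months

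*Protocol*

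**What the plan says.** Under Objectives and Endpoint, Hypothesis 2b is a statement about one year: "The 1-year follow-up rates of stroke within the target artery territory, non-traumatic hemorrhage, or neurologic death will be similar to that published" in the cited one-year trial.

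Under Outcomes, the matching primary outcome 2 is "Stroke within the territory treated, intracranial hemorrhage, or neurologic death within 6 months to 1 year after PTAS". Two procedures are required of every patient for it:

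- "Follow up clinic visit between 6 months to 1 year per standard of care";
- follow-up vascular imaging, with the modality left to the centre and no time point in that bullet.

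The list of variables repeats the 6-to-12-month window for both clinical and imaging data, and the secondary mRS outcome is set at days 180-360. Another secondary outcome is "Any death within 1 year after the procedure". No 12-month visit, call or record check appears in the document.

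The 72-hour outcome is handled differently. It has a fixed time point for all patients, and those already discharged are reached "by telephone interview by a core study nurse or interventionalist".

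The protocol also states "Study Duration: 2 years" without dividing that time between enrolment and follow-up.

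**The concern.** The hypothesis names a fixed horizon, while the outcome and its follow-up name a range. A centre that sees every patient at month 6 complies fully, yet observes only half of the year that the hypothesis concerns. The 1-year death outcome suggests that ascertainment to one year is intended, but no step delivers it.

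If nothing is learned after the visit and a crude proportion is reported, the registry's 1-year rate is understated by an amount set by centres' scheduling habits. A judgement that the registry is similar to its benchmark could then partly reflect visit timing.

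Two smaller ambiguities add to this. The wording does not exclude counting only events that occur in months 6-12, although that is the less natural reading. And if the two years include follow-up, a patient enrolled in months 13-18 can have a month-6 visit but cannot reach month 12 inside the study.

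**Working it through.** **The plan's own figure.** The only design number is 150 patients. No rate, margin, alpha or power is attached to it, so there is nothing to reproduce. What can be checked is the effect of visit timing.

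**Inputs.** From the protocol: n = 150; visit at any time in months 6-12; target horizon 12 months. Assumed, because the document gives no rates: true 1-year risk R = 10% (range 5-15%); risk p = 0 to 4 points by 72 hours; nothing ascertained after the visit; crude proportion reported.

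**Formula.** With t in years, F(t) = 1 - (1 - p)·exp(-H·t^k), where H = ln[(1 - p)/(1 - R)] so that F(1) = R. k = 1 is a constant hazard and k = 0.5 a front-loaded one. If all visits fall at month 6, the expected crude proportion is F(0.5). If visits are uniform over months 6-12, it is the mean of F over t from 0.5 to 1.

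**Worked case, R = 10%, p = 0, k = 1.** H = ln(1/0.90) = 0.1054.
- Month 6: 1 - exp(-0.0527) = 5.13%.
- Uniform: 1 - [exp(-0.0527) - exp(-0.1054)]/0.0527 = 1 - (0.9487 - 0.9000)/0.0527 = 7.59% (unrounded terms).

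**Crude proportion when the true 1-year risk is 10%** (ranges run from p = 0 to p = 4 points):

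| Hazard after 72 hours | Visits uniform, months 6-12 | All visits at month 6 |
|---|---|---|
| Constant | 7.59-8.53% | 5.13-7.05% |
| Front-loaded (k = 0.5) | 8.68-9.19% | 7.18-8.28% |

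For R from 5% to 15% with constant hazard, the crude proportion captures 75-95% of R with uniform visits and 51-90% with month-6 visits.

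**Partial record follow-up.** If records reach month 12 in a share s of patients, the expected proportion is s·R + (1 - s)·crude. With R = 10% and constant hazard:
- s = 0.5: 8.8-9.3% (uniform), 7.6-8.5% (month 6);
- s = 0.9: 9.8-9.9% and 9.5-9.7%;
- s = 1: no shortfall.

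For scale, the 95% half-width at 10% is 1.96·√(0.1·0.9/150) = 4.8 points.

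**Can the estimator repair it?** With uniform visits, only 150 × 1/6 = 25 patients have contact at or after month 11. Simulation with n = 150, uniform visits, R = 10%, p = 3 points (percentage points throughout):

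| Method | Constant hazard | Front-loaded hazard |
|---|---|---|
| Crude, no 12-month check | mean 8.3, RMSE 2.8 | mean 9.1, RMSE 2.5 |
| Kaplan-Meier, no check | mean 10.0, SE about 3.9-4.1 | mean 10.0, SE about 3.1-3.4 |
| 72-hour proportion plus constant hazard, no check | mean 10.0, RMSE 2.7 | mean 11.1, RMSE 3.1 |
| Kaplan-Meier, 12-month check in 80-90% | mean 10.0, RMSE 2.5 | mean 10.0, RMSE 2.5 |

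The check is taken to be obtained at random and to find all events. The Kaplan-Meier SE without a check varies somewhat between simulations, because few patients remain at risk near month 12.

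**Other risks.** At R = 5% (p = 2 points, constant hazard), RMSE is about 1.8 for both the crude proportion and Kaplan-Meier with the check. At R = 15% (p = 3 points), RMSE falls from 3.9 (constant) or 3.2 (front-loaded) to 2.9-3.0.

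**Literal months-6-12 reading.** With constant hazard and 0 to 50% of events at the procedure, an assumed 10% risk becomes 2.5-4.9%.

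**The case against.** The strongest reply is that the harm depends on two conditions the protocol does not set: that nothing is learned after the visit, and that a crude proportion is reported. The variable list asks for clinical data across months 6-12 and does not confine them to the visit. Treating centres may well hold later records, and record follow-up in 90% of patients leaves little shortfall. The estimator belongs to a SAP that is not shown, and Kaplan-Meier with censoring at the visit removes the bias if visit timing is unrelated to risk. Its loss of precision is partly driven by rare runs with an event among the last few patients at risk; an interquartile-based SD is nearer 3.0 (constant) and 2.7 (front-loaded). The window may also be a deliberate fit to a standard-of-care registry with an encouraged consent waiver, and similarity is stated without a margin, so no visible decision rule turns on a point or two.

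Much of this stands as a limit on size: the harm is conditional, the rates are assumed, and the gain in total error is small or nil at 5-10%. It does not remove the point. Endpoint timing and follow-up schedule are protocol content, and a SAP cannot create observations that the protocol does not require. Later records may exist, but nothing secures them.

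**Conclusion.** The point holds and should be fixed; confidence is medium. The mismatch between hypothesis and outcome is a matter of text and needs no assumption.

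Its numerical effect does rest on assumptions. At a true 1-year risk of 10%, with no ascertainment after the visit and a crude proportion, the understatement is about 0.8-2.4 points with uniform visits and 1.7-4.9 points with all visits at month 6, across both hazard shapes. Record follow-up to month 12 shrinks it, to zero if complete. A censored analysis avoids the bias, but without 12-month status it either loses precision or has to assume a hazard shape. The bias relative to the published benchmark cannot be judged from the protocol.

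The study-duration question is a request for clarification and would not stand as a point by itself.

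**What to change.** 1. Define primary outcome 2 as the first qualifying event from the procedure (day 0) through day 365. This also closes off the months-6-12-only reading.
2. Require 12-month status by chart review for any patient whose clinic visit falls earlier. The same check supports the 1-year death outcome.
3. Record the event date and the last known event-free date.
4. For Hypothesis 2b, use only the 12-month estimate, with censoring at last contact.
5. State whether the two years include follow-up, so that the last patient enrolled can reach month 12.

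**Cost.** Rewording, two date fields, and a chart check for patients seen early. Chart review can miss events treated elsewhere. A telephone check would catch more, and the protocol already uses telephone interviews at 72 hours, but at month 12 it is a contact beyond standard of care and needs IRB consideration given the encouraged waiver. If the two years include follow-up, 12-month status for everyone means enrolling within 12 months (150/12 = 12.5 per month, or 1.25 per centre at 10 centres) instead of 18 months (150/18 = 8.3, or 0.83 per centre), or else a longer study.

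Restating Hypothesis 2b to match the follow-up actually collected would cost less and would align the wording. It would give up the 1-year comparison and leave the 1-year death outcome without a step to ascertain it.

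### An early stent failure that is re-treated before month 6 can be counted as patent and not re-stenosed, because re-treatment is neither a named variable nor classified

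*Protocol*

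**What the plan says.** The Outcomes section lists two imaging measures among the secondary outcomes: "Stent patency on follow up vascular imaging" and "Re-stenosis ≥ 70% on follow up vascular imaging". Neither line gives a time window or says what happens to a stent that has been treated again.

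Under the second primary outcome, patients are to have a "Follow up clinic visit between 6 months to 1 year per standard of care" and follow-up vascular imaging, for which the "modality of imaging will be decided based on standard of care at participating centers". The time window for the imaging itself appears in the Variables collected section, which lists "follow up vascular imaging data between 6-12 months post procedure, follow up clinical data between 6-12months post procedure".

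That section does not name repeat angioplasty, repeat stenting or any other re-treatment of the target lesion, nor imaging done before month 6. The nearest entry is "intraprocedural and post procedural complications, degree of residual stenosis", in which complications have neither a definition nor a time limit. The planned size is given as "Sample Size: 150 patients".

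**The concern.** Patency and re-stenosis are the only delayed imaging outcomes listed, and Aim 2 sets up the registry for "evaluating current periprocedural and delayed outcomes for PTAS in patients with medically refractory ICAD". Consider a patient with transient symptoms at month 3, whose scan shows at least 70% in-stent stenosis and whose stent is reopened. That scan lies outside the listed window and the re-treatment has no named place. If the vessel is open at month 8, the listed imaging data show a patent stent without re-stenosis. With no stroke, hemorrhage or death, no primary outcome registers the failure either.

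The patients affected are early failures serious enough to be re-treated, so the error does not average out: it makes stenting look more durable than it was. An analysis plan cannot fully repair this. It can set a rule for re-treated stents, but can apply that rule only where the re-treatment was recorded.

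**Working it through.** The protocol gives no re-stenosis rate, re-treatment rate, power or margin, so it has no figure to reproduce. The first part of the check compares the texts; the second illustrates size.

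**Following the text for one stent**

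1. The stent reaches at least 70% stenosis, or occludes, before month 6. Imaging at that time is outside the window in Variables collected.
2. It is re-treated before month 6. Variables collected names no such item, and Outcomes has no such event.
3. The scan between 6 and 12 months is read. If the vessel is open and below 70%, both outcomes are scored as favourable.
4. The failure is visible only if the center entered it under complications or follow-up clinical data. Neither entry asks for it.

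**Illustration of size**

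Only N = 150 comes from the protocol. The other inputs are assumptions:

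- r: share of patients with at least 70% re-stenosis or occlusion at any time up to month 12 (10-30%)
- f: share of those re-treated before month 6 (10-50%)
- g: share of the re-treated again at 70% or more at the 6-12 month scan (0-30%)

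It is also assumed that every patient is imaged and that no center reports the re-treatment elsewhere.

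Recorded rate = r(1 − f) + r·f·g. Missed patients = N·r·f·(1 − g).

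| r | f | g = 0: recorded rate (missed) | g = 30%: recorded rate (missed) |
|---|---|---|---|
| 10% | 10% | 9.0% (1.5) | 9.3% (1.05) |
| 10% | 50% | 5.0% (7.5) | 6.5% (5.25) |
| 20% | 25% | 15.0% (7.5) | 16.5% (5.25) |
| 30% | 10% | 27.0% (4.5) | 27.9% (3.15) |
| 30% | 50% | 15.0% (22.5) | 19.5% (15.75) |

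- Smallest: 150 × 0.10 × 0.10 × 0.70 = 1.05 patients, or 0.7 percentage points.
- Largest: 150 × 0.30 × 0.50 × 1 = 22.5 patients, or 15 percentage points.
- With f = 0 the missed number is 0 whatever r and g are.

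The missed number is never negative, so under these assumptions the error can only lower the recorded re-stenosis rate. For patency the same argument applies to the failures that were occlusions.

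**The case against.** The strongest reply is that the list of variables is a summary and not a field dictionary. It does not name recurrent stroke, intracranial hemorrhage, death or myocardial infarction separately either, although all are outcomes. These must sit under broad entries such as 72-hour clinical status, complications and follow-up clinical data. Re-treatment could sit there too, and the REDCap form is not shown. This stands in part: one cannot say that re-treatment goes unrecorded. But the listed outcomes at least tell centers what to look for, and re-treatment is not among them. With up to 10 centers, each following its own standard of care, reporting would be left to chance.

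Second, an outcome read on follow-up imaging can fairly mean status at that scan, not whether the stent ever failed. That is a legitimate estimand. It still needs a rule for a stent that is open only because it was treated again, and the protocol has none. Adding symptom-driven scans also brings in detection differences between centers, so both measures should be reported.

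Some stronger readings are tempting but unsupported:

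- A reader might infer that the protocol rules re-treated stents to be successes. It states no such rule. The misclassification is possible, not prescribed, and needs the vessel to be open and below 70% at the later scan.
- A reader might infer that Aim 1 is distorted by device. Aim 1 and Hypothesis 1 concern which devices are used, and misreading re-stenosis does not change that count.
- A reader might add patients who die before month 6. They have no reading and are not scored patent. Their deaths are captured by the one-year death outcome, and the handling of missing readings may be left to the analysis plan.

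**Conclusion.** The point holds as a gap in data collection and classification. On the data as listed, a stent that fails and is re-treated before month 6 can be counted as patent and not re-stenosed, unless a center volunteers the event. The direction is certain where this happens: re-stenosis too low, patency too high.

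The size cannot be derived from the protocol. About 1 to 22.5 patients of 150 follows from the assumed ranges and from assuming complete imaging with no reporting elsewhere; with no early re-treatment the error is zero.

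A reader might go on to doubt the primary results. The protocol does not support that: neither primary composite, nor Hypotheses 2a and 2b, uses patency or re-stenosis. This is a worthwhile, inexpensive improvement to two secondary outcomes, not a flaw in the main comparisons.

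**What to change.** 1. Add REDCap fields for any target-lesion re-treatment: yes or no, days from the procedure, and reason. Days rather than dates suit the plan to collect deidentified data.
2. Add a field for the finding of any target-vessel imaging already done in routine care before month 6, flagged as routine or symptom-driven. No scan is added.
3. State in the outcome definition that re-treatment for re-stenosis or occlusion, or documented re-stenosis of at least 70% or occlusion before month 6, counts as a re-stenosis or loss-of-patency event whatever a later scan shows.
4. Report status at the 6-12 month scan alongside this, so that both measures are visible.
5. Report separately the patients who died or otherwise had no follow-up imaging by month 12.

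The cost is a few more fields, a short addition to the outcome definition, and possibly some extra core-lab reading if early scans are to be read centrally. The reported re-stenosis rate will be less favourable, and symptom-driven scans will bring some detection differences between centers, which the flag makes visible but does not remove. Early failures not recorded as they occur may be hard to recover later.
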